8.10.3 Physical Examination

Physical exam results will include the assessment of general appearance; head, eyes, ears, nose, and throat (HEENT); the cardiovascular, dermatology, lymphatic, respiratory, gastrointestinal, genitourinary, musculoskeletal, and neurological systems. The number and percentage of subjects with Normal/Abnormal assessment for each body system will be summarized by visit. All physical examination assessments will be listed.

8.10.4 Vital Signs

Blood pressure measurements will be obtained only in children aged 3 and 4 years of age and will only be obtained at clinic visits. The blood pressure will be summarized by study visit in mmHg and percentile to assess the blood pressure change over time. The average of the triple measurements will be used in the summary.

Heart rate and heart rate percentile category will also be summarized by study visit.

8.10.5 Renal Ultrasound

Renal ultrasound will be conducted with findings of nephrocalcinosis graded on a 5-point scale by a central reader. The renal ultrasound is read using a pre-defined methodology ([Biomedical Systems Independent Review Manual November 2014](#)). These results will be summarized by time point, a grade shift table summarizing changes from Baseline by time point will also be created.

8.10.6 Electrocardiogram

Descriptive statistics for ECG parameters (heart rate, RR interval, PR interval, QRS duration, QT interval, and QTc) and changes from baseline values at each assessment time point to the end of study will be presented by. The QTc will be calculated using both the Bazett and Fridericia corrections.

ECG parameters will be summarized by the maximum post-baseline value and maximum change from baseline using the following categories based on FDA guidance (FDA 2015) listed in Table 8.10.6.1.

Table 8.10.6.1: Criteria for ECG Results

ECG Parameter	Categories for Baseline and Maximum Post-Baseline Value	Categories for Maximum Change from Baseline Value
PR Interval	≤ 200 and >200 msec	≤ 20 and >20 msec
QRS Interval	≤ 110 and >110 msec	≤ 10 and >10 msec
QTc Interval	≤ 450 , >450 - ≤ 480 , >480 - ≤ 500 and >500 msec	≤ 30 , >30 - ≤ 60 and >60 msec

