3.1 Study Population

UX023-CL205 is a multicenter, open-label, Phase 2 study in children from 1 to 4 years old with XLH who are naïve to therapy or have previously received standard therapy with oral phosphate and active vitamin D to assess the safety, PD, and efficacy of KRN23 administered via subcutaneous injections Q2W for a total of 64 weeks.

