3.5 Sample Size Considerations

The study will enroll approximately 10 pediatric subjects between 1 and 4 years old, inclusive, with clinical findings consistent with XLH including hypophosphatemia and radiographic evidence of rickets (at least 5 subjects will have a rickets severity score (RSS) at the knee of ≥ 1.5 points at Screening), and a confirmed *PHEX* mutation or variant of uncertain significance. To maintain a level of gender balance, no more than 7 subjects of either gender will be enrolled.

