4.4 Safety Endpoints

General Safety Variables will include the following:

- Treatment Emergent Adverse Events (TEAEs)
- Treatment Related TEAEs
- Treatment Emergent Serious Adverse Events (TESAEs)
- Events to monitor:
 - Injection site reaction (High-Level Term)
 - Immunogenicity

- Hyperphosphatemia
- Ectopic mineralization
- Restless leg syndrome
- Grade 3/4 TEAEs
- TEAEs leading to discontinuation from the study
- TEAEs leading to discontinuation from the study drug treatment
- TEAEs leading to death
- Vital signs and weight
- Physical examinations
- Estimated Glomerular Filtration Rate (eGFR)
- Chemistry, hematology, and urinalysis, including additional KRN23/XLH biochemical parameters of interest (serum calcium, intact parathyroid hormone[iPTH], 25-hydroxyvitamin D [25(OH)D], amylase, lipase, and creatinine; and urinary calcium and creatinine)
- FGF23
- Anti-KRN23 antibody (HAHA) testing and Dose-Limiting Toxicities (DLT)
- Concomitant medications

Ectopic Mineralization Safety Assessments include:

- Renal ultrasound
- Electrocardiogram (ECG)

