5.8 Heart Rate Percentile

The heart rate percentile category will be derived based on the National Health Statistical Reports on resting pulse rate reference data for children, adolescents, and adults: United States, 1999-2008 ([Ostchega et al. 2011](#)). See [Appendix 7](#) for details in deriving heart rate percentile category adjusting for age and gender.

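### ECG category table: absolute PR and QRS limits are not age-referenced for children aged 1 to 4, and the single QTc row does not say which of two corrections it uses

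*SAP*

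**What the plan says.** The trial is an "open-label, Phase 2 study in children from 1 to 4 years old with XLH" (SAP 3.1), and "The study will enroll approximately 10 pediatric subjects between 1 and 4 years old, inclusive" (3.5). Establishing the safety profile at this age is a primary objective (2.1), and there is no comparator arm (3.3). Section 4.4 has a list opening "Ectopic Mineralization Safety Assessments include", which holds two items: renal ultrasound and ECG.

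For ECG, section 8.10.6 plans:
- descriptive statistics of heart rate, RR, PR, QRS, QT and QTc, with changes from baseline, at each time point;
- a categorical summary of the maximum post-baseline value and the maximum change, "using the following categories based on FDA guidance (FDA 2015) listed in Table 8.10.6.1".

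The absolute categories in Table 8.10.6.1 are "≤ 200 and >200 msec" for PR, "≤ 110 and >110 msec" for QRS, and cut-offs at 450, 480 and 500 msec for QTc. The change categories cut at 20 msec (PR), 10 msec (QRS), and 30 and 60 msec (QTc). None varies with age. The cited guidance has no entry in the section 9 reference list.

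On the correction, "The QTc will be calculated using both the Bazett and Fridericia corrections", but the table has one QTc row and names neither.

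Other cardiovascular measurements are handled differently. Blood pressure is converted to a percentile for age, gender and height (5.7). Section 5.8 points to an appendix for "deriving heart rate percentile category adjusting for age and gender". Both are summarised by visit under 8.10.4.

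**The concern.** The SAP accepts that blood pressure and heart rate in children this young must be read against age, yet it sorts their conduction intervals on a single limit without giving a reason. If normal intervals at this age lie well below 200 and 110 msec, a value that is long for the child's age stays in the lowest category. In a single-arm trial these absolute limits are the only external benchmark in the ECG analysis, so an empty column could be taken as reassurance that it cannot give.

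The QTc problem is one of specification. The two corrections diverge as heart rate rises, so a table that does not name its correction can be produced in two ways from the same data, with different counts in each category.

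**Working it through.** The SAP states no error rate or expected count for this table, so there is no figure of its own to reproduce.

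**1. Absolute PR and QRS columns**

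Inputs from the SAP: limits of 200 and 110 msec (8.10.6), about 10 children (3.5), and 3 post-baseline ECGs each (Appendix 3: one before Week 30, then Weeks 40 and 64).

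Assumed, not in the SAP: PR mean 110-140, SD 15-20 msec; QRS mean 60-80, SD 8-10 msec; normal distributions; independent readings. Positive correlation within a child would lower the chance of any exceedance.

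Formulas: z = (limit - mean)/SD; p = 1 - Φ(z); chance of at least one exceedance in 10 × 3 = 30 readings = 1 - (1 - p)^30.

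| Interval | Mean, SD (assumed) | z | p | At least one in 30 |
|---|---|---|---|---|
| PR | 140, 20 | 60/20 = 3.0 | 0.00135 | 4.0% |
| PR | 130, 20 | 70/20 = 3.5 | 0.00023 | 0.7% |
| PR | 110, 15 | 90/15 = 6.0 | below 0.00001 | below 0.1% |
| QRS | 80, 10 | 30/10 = 3.0 | 0.00135 | 4.0% |
| QRS | 75, 10 | 35/10 = 3.5 | 0.00023 | 0.7% |
| QRS | 60, 8 | 50/8 = 6.25 | below 0.00001 | below 0.1% |

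A low exceedance rate in unaffected children would be welcome if the limit were still within reach of an affected child. Under these assumptions it is far off. A child at the mean must lengthen PR by 60 to 90 msec, or QRS by 30 to 50 msec, to reach the limit. A PR two SDs above the mean is 110 + 2×15 = 140 to 140 + 2×20 = 180 msec; the corresponding QRS is 60 + 2×8 = 76 to 80 + 2×10 = 100 msec. All of these stay in the lowest category.

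**2. Change-from-baseline columns for PR and QRS**

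Assumed within-child SD s: PR 6-12 msec, QRS 3-6 msec. With no drug effect, p = 1 - Φ(cut-off/(s√2)).
- Smallest s: 20/(6√2) = 10/(3√2) = 2.36, p = 0.0092, and 1 - (1 - 0.0092)^10 = 9%.
- Largest s: 20/(12√2) = 10/(6√2) = 1.18, p = 0.119, and 1 - (1 - 0.119)^10 = 72%.

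So at a single visit the chance that at least one of 10 children crosses the change limit is 9% to 72%. These columns compare each child with itself and can register events at any age.

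**3. QTc row**

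Bazett: QTcB = QT/RR^(1/2). Fridericia: QTcF = QT/RR^(1/3). Hence QTcB/QTcF = RR^(-1/6), with RR = 60/heart rate in seconds. Heart rates and QTcF values are assumed.

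| Heart rate | RR (s) | Ratio | QTcB if QTcF 400 | QTcB if QTcF 420 | QTcB if QTcF 450 |
|---|---|---|---|---|---|
| 100 | 0.600 | 1.089 | 436 | 457 | 490 |
| 120 | 0.500 | 1.122 | 449 | 471 | 505 |
| 140 | 0.429 | 1.152 | 461 | 484 | 518 |

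By Fridericia every entry is in the lowest category (at most 450 msec). By Bazett, a QTcF of 400 at 140 bpm is one category higher, 420 at 140 bpm is two higher, and 450 at 120 bpm is three higher.

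**The case against.** The strongest reply is that this table is one descriptive display with no test or decision rule attached. The raw intervals and their changes are summarised at each time point (8.10.6), all data are listed (8.1), about 10 children can be read one by one, and the monitoring committee includes cardiology expertise (3.7). This stands and limits the harm, but none of these outputs supplies an age benchmark.

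It is also fair that the SAP gives no paediatric PR, QRS or heart rate values. The size of the problem therefore rests on assumptions, and the cited guidance cannot be consulted from the SAP.

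On QTc, the natural reading may be that the categories are to be applied to each correction. Then the row is unclear rather than wrong, and labelling it settles the matter.

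A reader might be tempted by stronger conclusions that the document does not support:
- *The PR and QRS table will be empty.* This could apply at most to the absolute columns; the change columns can register events, as the working shows.
- *Bazett will hide prolongation over 64 weeks as heart rate slows.* At a constant QTcF of 400 msec, slowing from 120 to 105 bpm (assumed) lowers QTcB from 449.0 to 439.1, about 10 msec against a 30 msec threshold. The argument treats constant QTcF as unchanged repolarisation, which presumes that Fridericia is correct at this age. The table uses the maximum change, and Fridericia is computed as well.
- *Fridericia should lead.* Nothing in the SAP ranks the two corrections.
- *Blood pressure and heart rate already use an age-based outlier flag.* The SAP text summarises percentiles and percentile categories and states no outlier cut-off for either.

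**Conclusion.** The point holds in a limited form. The text itself shows that the ECG limits are fixed across ages while blood pressure and heart rate are age-referenced, and that one QTc row serves two corrections. The ratio between the corrections is exact; its size of 9% to 15% depends on the assumed range of 100 to 140 bpm.

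That the absolute PR and QRS columns are likely to be uninformative (below 0.1% to 4% chance of any exceedance) depends on the assumed interval distributions and would weaken if intervals in this age group lie closer to the limits. The consequence is a weak benchmark and an ambiguous row in a descriptive safety display. It is worth correcting because safety is a primary objective and there is no control arm, but it does not invalidate the ECG analysis.

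**What to change.** In section 8.10.6:
1. Add PR and QRS categories based on age-specific upper limits from a named paediatric reference chosen by the sponsor, applied at the child's age on the ECG date.
2. Keep the change-from-baseline columns, and keep the fixed-limit table as a supplement.
3. Present the QTc categories in two labelled rows, one for Bazett and one for Fridericia, for both the absolute and the change columns.
4. Add the cited guidance to section 9 so that the origin of the fixed limits can be checked.

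The cost is SAP wording and one lookup table; no new data are needed. The small downside is less direct comparison with studies that used only fixed limits, which keeping the supplementary table largely offsets.

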10 APPENDICES

Appendix 1: Efficacy Endpoint Summary Table

Endpoints	Scale	Analysis Set	Comparisons	Data Time Points	Week 40 Analysis	Week 64 Analysis
Serum phosphorus	Continuous	PK/PD	Baseline vs. Post-baseline	Refer to Schedule of Events (Appendix 3)	GEE Descriptive Statistics	GEE Descriptive Statistics
RGI-C wrist, knee, global and lower limb deformity scores	Continuous Categorical	Efficacy	Baseline vs. Post-baseline	Baseline, Week 40, 64	GEE Descriptive Statistics	GEE Descriptive Statistics
RSS knee, wrist and total scores	Continuous	Efficacy	Baseline vs. Post-baseline	Baseline, Week 40, 64	GEE Descriptive Statistics	GEE Descriptive Statistics
Growth (standing height/recumbent length)	Continuous	Efficacy	Baseline vs. Post-baseline	Baseline, Week 12, 24, 40, 64	GEE Descriptive Statistics	GEE Descriptive Statistics
Other PD parameters	Continuous	PK/PD	Baseline vs. Post-baseline	Refer to Schedule of Events (Appendix 3)	Descriptive Statistics	Descriptive Statistics

Appendix 2: Clinical Laboratory Assessments for Safety

Chemistry	Hematology	Urinalysis¹
1,25(OH) ₂ D ²	Hematocrit	Appearance
25(OH) ₂ D	Hemoglobin	Color
Alanine aminotransferase (ALT)	Platelet count	pH
Alkaline phosphatase (ALP) ²	Red blood cell (RBC) count	Specific gravity
Amylase	White blood cell (WBC) count	Ketones
Aspartate aminotransferase (AST)	Mean corpuscular volume (MCV)	Protein
Bilirubin (direct and total)	Mean corpuscular hemoglobin (MCH)	Glucose
Blood urea nitrogen (BUN)	MCH concentration	
Calcium (total)		
Chloride		
Carbon dioxide (CO ₂)		
Cholesterol (total)		
Creatinine		
Gamma-glutamyl transpeptidase (GGT)		
Glucose		
FGF23		
Intact parathyroid hormone (iPTH)		
Lactate dehydrogenase (LDH)		Spot Urine
Lipase		Calcium
Phosphorus ²		Creatinine

Chemistry	Hematology	Urinalysis ¹
Potassium		Phosphorus
Protein (albumin and total)		
Sodium		
Uric acid		

¹Urinalysis to be conducted if possible based on urine volume collected.

²Also designated as a PD/efficacy parameter

Appendix 3: Schedule of Events

Table 10.1: Schedule of Events – Screening, Baseline, and Treatment Period Weeks 1-30

VISIT TYPE/NUMBER	Screening/ Baseline ¹		Treatment Period ³																	
	SV	BL V1 ²	HH V2	HH V3	V4	HH V5	V6	HH V7	V8	HH V9	V10	HH V11	HH V12	V13	HH V14	V15	HH V16	HH V17	HH V18	
WEEK	W -6 to BL	W0	W1	W2	W4	W6	W8	W 10	W 12	W 14	W 15	W 16	W 18	W 20	W 22	W 24	W 26	W 28	W 30	
Informed Consent	X																			
Inclusion/Exclusion Criteria	X	X																		
Medical History & Demographics	X																			
PHEX mutation analysis ⁵	X																			
PD MEASURES																				
Serum Phosphorus ⁶		X	X		X		X		X		X		X		X					
1,25(OH) ₂ D ⁶		X	X							X					X					
Spot urine ^{6,7}		X			X					X		X			X					
ALP only ⁶		X													X					
EFFICACY MEASURES																				
Growth (recumbent length/standing height)			X							X						X				
Bilateral AP knee X-rays ²	X																			
Bilateral PA hand/wrist ²		X																		
Standing long leg X-Ray ²		X																		
PHARMACOKINETICS																				
Serum Pre-Dose KRN23 ⁶			X		X				X											

VISIT TYPE/NUMBER	Screening/ Baseline ¹		Treatment Period ³																		
	SV	BL V1 ²	HH ⁴ V2	HH V3	V4	HH V5	V6	HH V7	V8	HH V9	V10	HH V11	HH V12	V13	HH V14	V15	HH V16	HH V17	HH V18		
WEEK	W -6 to BL	W0	W1	W2	W4	W6	W8	W 10	W 12	W 14	W 15	W 16	W 18	W 20	W 22	W 24	W 26	W 28	W 30		
SAFETY																					
Vital Signs ^{8,9}	X	X	X	X	X	X	X	X	X	X	X	X	X	X	X	X	X	X	X	X	
Weight	X	X			X					X							X				
Physical Examination	X	X																X			
Concomitant Medications	X	X	X	X	X	X	X	X	X	X	X	X	X	X	X	X	X	X	X	X	
Adverse Events	X	X	X	X	X	X	X	X	X	X	X	X	X	X	X	X	X	X	X	X	
Renal Ultrasound ²	X																				
ECG ²		X									X										
Chemistry, Hematology, Urinalysis ^{6,7,10}	X	X			X						X						X				
Serum 25(OH)D ⁶	X										X										
Serum Calcium ⁶	X	X	X		X		X			X		X				X					
Serum Creatinine ⁶	X	X			X					X		X				X					
Serum iPTH ⁶	X	X								X						X					
Serum FGF23 ⁶		X																X			
Anti-KRN23 antibody (HAHA) ^{6,11}		X			X					X											
DRUG ADMINISTRATION		X		X	X	X	X	X	X	X	X	X	X	X	X	X	X	X	X	X	

See footnotes after [Table 10.2](#)

Table 10.2: Schedule of Events – Treatment Period Weeks 32 – 64

Visit Type/Number	Treatment Period ³																		Safety Visit ¹³	
	V19	HH V20	HH V21	HH V22	V23	HH V24	HH V25	HH V26	V27	HH V28	HH V29	HH V30	V31	HH V32	HH V33	HH V34	V35	V36		
Week	W 32	W 34	W 36	W 38	W 40	W 42	W 44	W 46	W 48	W 50	W 52	W 54	W 56	W 58	W 60	W 62	W 64/ ET ¹²	W 76		
PD MEASURES																				
Serum Phosphorus ⁶	X					X				X				X					X	X
1,25(OH) ₂ D ⁶	X					X				X				X					X	X
Spot urine ^{6,7}	X					X				X				X					X	X
ALP only ⁶						X													X	
EFFICACY MEASURES																				
Growth (length/standing height)						X													X	
Bilateral AP knee X-rays ²						X													X	
Bilateral PA hand/wrist X-rays ²						X													X	
Standing long leg X-ray ²						X													X	
PHARMACOKINETICS																				
Serum Pre-Dose KRN23 ⁶						X														
SAFETY																				
Vital Signs ^{8,9}	X	X	X	X	X	X	X	X	X	X	X	X	X	X	X	X	X	X	X	
Weight	X					X				X				X						
Physical Examination						X													X	X
Concomitant Medications	X	X	X	X	X	X	X	X	X	X	X	X	X	X	X	X	X	X	X	
Adverse Events	X	X	X	X	X	X	X	X	X	X	X	X	X	X	X	X	X	X	X	

Visit Type/Number	Treatment Period ³																	Safety Visit ¹³
	V19	HH V20	HH V21	HH V22	V23	HH V24	HH V25	HH V26	V27	HH V28	HH V29	HH V30	V31	HH V32	HH V33	HH V34	V35	
Week	W 32	W 34	W 36	W 38	W 40	W 42	W 44	W 46	W 48	W 50	W 52	W 54	W 56	W 58	W 60	W 62	W 64/ ET ¹²	W 76
Renal Ultrasound ²					X													X
ECG ²					X													X
Chemistry, Hematology, Urinalysis ^{6,7,10}					X				X				X					X X
Serum 25(OH)D ⁶					X													X
Serum Calcium ⁶	X				X				X				X					X X
Serum Creatinine ⁶	X				X				X				X					X
Serum iPTH ⁶					X													X
Serum FGF23 ⁶																		X
Anti-KRN23 antibody (HAHA) ^{6,11}					X													
DRUG ADMINISTRATION	X	X	X	X	X	X	X	X	X	X	X	X	X	X	X	X		

¹ The baseline visit may occur up to approximately 6 weeks after Screening in those subjects without a previously documented *PHEX* mutation to allow for *PHEX* mutation results to be determined

² All Screening/Baseline assessments and inclusion/exclusion criteria based on local lab results must be satisfied prior to randomization and dosing. Renal ultrasound, ECG, and x-rays may be performed within \pm 3 days of clinic visit to accommodate scheduling availability.

³ Subjects will return to the clinic for site visits at approximately 4-week intervals from Baseline to Week 24 and at 8-week intervals from Week 24 to Week 64. The visit window is \pm 3 days

⁴ Home health (HH) visits may also be conducted at the clinic depending on proximity of the subject to the investigational site and local availability of home health care resources. The visit window is \pm 3 days.

⁵ *PHEX* mutation analysis will be performed for all subjects. Potential subjects with prior confirmation of a *PHEX* mutation or variant of uncertain significance in either self or a family member with appropriate X-linked inheritance who meet other eligibility requirements may enroll before screening *PHEX* mutation results are returned.

- 6 Blood and urine to be collected after a minimum fasting time of 4 hours and prior to drug administration (if applicable). Record fasting duration on CRF. Subjects who live more than 45 minutes from the site may stay overnight on the night before the site visit to facilitate fasting sample collection. At Baseline, local lab values will be used to confirm eligibility. Baseline samples will also be sent to the central lab for data analysis. Serum phosphorus may be collected as an unscheduled lab if necessary
- 7 Spot urine collections for urinary calcium, phosphorus, and creatinine
- 8 At site visits, vital sign measurements consist of seated systolic/diastolic blood pressure (BP) measured in millimeters of mercury (mm Hg), heart rate (HR; beats per minute), respiration rate (breaths per minute), and temperature in degrees Celsius (°C). Blood pressure will only be obtained for subjects age 3 or 4 years. Obtain HR, respiration rate, and temperature at the beginning of each visit before any additional assessments are completed. At the Screening Visit BP should be measured 3 times, 30 seconds apart at the beginning of each visit; 3 additional BP measurements, 30 seconds apart, should be obtained at the end of the study visit after all procedures have been performed. At baseline and post-baseline visits, 3 BP measurements 30 seconds apart, should be obtained at the beginning of the study visit.
- 9 At HH visits, vital sign measurements consist of HR (beats per minute) and temperature in degrees Celsius (°C). Obtain at the beginning of each visit before any additional assessments are completed.
- 10 Serum chemistry panels may include PD parameters (i.e., serum phosphorus and ALP), and safety parameters of interest (i.e., calcium) to avoid duplication of testing. Urinalysis will be conducted if possible based on urine volume collected.
- 11 If the development of anti-KRN23 antibodies is suspected in a given subject, samples may be obtained at additional time points on a case-by-case basis, if warranted.
- 12 Radiography (x-rays) will not be performed at the early termination (ET) visit if the assessment was conducted within 3 months of termination.
- 13 An additional safety visit will take place 12 weeks ± 1 week after the date of the last study drug administration for those subjects who discontinue treatment, or 12 weeks ± 1 week after the Week 64 visit for subjects who complete the study and choose not to enroll immediately in an extension study. This visit is not required for subjects who are eligible and choose to take part in an extension study. Every reasonable effort should be made to have required subjects return to the clinic for the final safety visit; however, subjects who are unable to return to the clinic for the final safety visit will be given the option of providing blood and urine samples as part of a HH visit.

Appendix 4: RSS Data Collection Form

WRIST

GRADE DEFINITIONS FOR RADIUS AND ULNA *based on radiographic features below*

1	Widened growth plate, irregularity of metaphyseal margin, but without concave cupping
2	Metaphyseal concavity with fraying of margins

Grade radius
circle 1 or 2

RADIUS	1
	2

Grade ulna
circle 1 or 2

ULNA	1
	2

Radius Grade Ulna Grade TOTAL POINTS FOR WRIST *(max of 4 points possible)*

+ = WRIST TOTAL

KNEE

GRADE DEFINITIONS FOR FEMUR AND TIBIA		based on the degree of lucency and widening of zone of provisional calcification
1	Partial lucency, smooth margin of metaphysis visible	
2	Partial lucency, smooth margin of metaphysis NOT visible	
3	Complete lucency, epiphysis appears widely separated from distal metaphysis	

Grade femur circle 1, 2, or 3	FEMUR	1	Determine multiplier for femur circle 0.5 or 1	Based on portion of growth plate affected	
		2		≤ one condyle or plateau affected	0.5
		3		Two condyles or plateaus affected	1
Grade tibia circle 1, 2, or 3	TIBIA	1	Determine multiplier for tibia circle 0.5 or 1	Based on portion of growth plate affected	
		2		≤ one condyle or plateau affected	0.5
		3		Two condyles or plateaus affected	1

Femur Grade Multiplier Tibia Grade Multiplier Total points for KNEE (*max of 6 points possible*)

X + X = KNEE TOTAL

